2.0	28Feb2022	[Redacted]	
Section 7.4 Included details of deriving -azole resistance subcategory using local laboratory data, since central lab data was not available for all patients.
 
Section 12.1 Included details for imputation of partial and missing dates for medications.
 
Section 14 Added categories Duration of exposure details.
 
Section 16.1.7.5 Added details for ascertaining survival status where survival status was not collected in the eCRF.
 
Section 16.1.7.5 Added specification that Kaplan-Meier plots will be truncated when the number of patients at risk is <5. This is due to large degree of uncertainty leading to potentially misleading interpretation.
 
Section 18.4.2 Systolic Blood Pressure markedly abnormal high criteria amended to ≥ 140 mmHg based on advice from safety physicians.

Document: \\weedc-vnasc01\BIOSdata\F2G\F901318 [Redacted]
 Author: [Redacted] Version Number: 3.0
 Version Date: 06Apr2023
 Template No.: CS_TP_BS016 Revision 6 Reference: CS_WI_BS005
 Effective Date: 02Dec2019

F2G Ltd.
PROTOCOL F901318/0032

3.0	17Mar2023		
Section 7.4 added subgroup for Reason for Limited Treatment Options and updated neutropenia status derivation.
 
Section 17 added subgroups (concomitant medication, demographaics and underlying disease)
 
Sectoin 17.1 further defined acceptabel sampling widnow for trough samples
 
Section 17.1.1 revised analysis for assessing impact of concomitant medications upon olorofim exposure
 
Section 18.2.1 added derivation for Creatinine clearance
 
Section 18.3.2 added definition of retrospective and prospective ECG overreads.

-----	-----------	--	---

Document: \\weedc-vnasc01\BIOSdata\F2G\F901318

Author: Version Number: 3.0

Version Date: 06Apr2023

Template No.: CS_TP_BS016 Revision 6 Reference: CS_WI_BS005

Effective Date: 02Dec2019

F2G Ltd.
PROTOCOL F901318/0032

TABLE OF CONTENTS

1.	INTRODUCTION	12
2.	STUDY OBJECTIVES AND ESTIMANDS	12
2.1.	Primary Objective	12
2.2.	Secondary Objectives	12
2.3.	Exploratory Objectives	13
2.4.	Extended Treatment Exploratory Objectives	13
2.5.	Estimands	13
3.	STUDY DESIGN	13
3.1.	General Description	13
3.2.	Schedule of Events	17
3.3.	Changes to Analysis from Protocol	17
4.	PLANNED ANALYSES	18
4.1.	Independent Data & Safety Monitoring Board (IDSMB)	19
4.2.	DRC Analyses	19
4.3.	Analyses for initial CSR	19
4.4.	Final Analysis	20
5.	ANALYSIS SETS	20
5.1.	Process for Analysis Set Assignment	20

1. INTRODUCTION

This document describes the rules and conventions to be used in the presentation and analysis of efficacy, pharmacokinetic (PK) and safety data for protocol F901318/0032. It describes the data to be summarised and analysed, including specifics of the statistical analyses to be performed.

This statistical analysis plan (SAP) is based on protocol version 01 dated 19 Dec 2017, amendment 01 dated 24 Jan 2018, amendment 01-01 dated 07 Mar 2018, amendment 02 dated 02 May 2018, amendment 03 dated 28 Nov 2018, amendment 4 dated 03 May 2019, amendment 5 dated 30 Oct 2019 and amendment 6 dated 28 Feb 2020. However protocol amendment 5 has no impact on the SAP.

A data review (DR) plan will be set up for this study and will pertain to the SAP.

2. STUDY OBJECTIVES AND ESTIMANDS

2.1. PRIMARY OBJECTIVE

The primary objective is:

To describe the Data Review Committee (DRC)-adjudicated efficacy of F901318 as treatment for infections due to resistant fungi in patients lacking suitable alternative treatment options.

2.2. SECONDARY OBJECTIVES

The secondary objectives are:

- To describe the safety of F901318 as treatment for infections due to *Lomentospora prolificans*, *Scedosporium* spp., *Aspergillus* spp., and other resistant fungi in patients lacking suitable alternative treatment options.
- To describe the efficacy of F901318 in terms of Investigator-assessed overall response (integrating clinical, radiological and mycological response).
- To describe all-cause mortality.
- To characterize PK of study drug and metabolite(s) including effects of dose adaptations.
- To evaluate patient-reported outcomes based on the European quality of life – 5 dimensions (EQ-5D-5L)

Document: \\ieedc-vnasc01\BIOSdata\F2G\F901318 [Redacted]
Author: [Redacted] Version Number: 3.0
Version Date: 06Apr2023
Template No.: CS_TP_BS016 Revision 6 Reference: CS_WI_BS005
Effective Date: 02Dec2019

F2G Ltd.
PROTOCOL F901318/0032

[figure not shown]
questionnaire.

2.3. EXPLORATORY OBJECTIVES

The exploratory objectives are:

- To evaluate dose adaptation and drug-drug interaction (DDI) management strategies.
- To assess potential drug interactions associated with F901318 treatment.

2.4. EXTENDED TREATMENT EXPLORATORY OBJECTIVES

2.5. ESTIMANDS

Not applicable.

3. STUDY DESIGN

3.1. GENERAL DESCRIPTION

This is an open-label, single-arm, Phase IIb study to evaluate the efficacy, safety, tolerability and PK profile of F901318 in patients with fungal infections lacking suitable alternative treatment options. The rate of enrolment into the study is likely to be low, and it is anticipated that approximately 200 patients will be enrolled at approximately 100 centres globally over at least 60 months.

Document: \\ieedc-vnasc01\BIOSdata\F2G\F901318 [redacted]
Author: [redacted] Version Number: 3.0
Version Date: 06Apr2023
Template No.: CS_TP_BS016 Revision 6 Reference: CS_WI_BS005
Effective Date: 02Dec2019

F2G Ltd.
PROTOCOL F901318/0032

Patients will have invasive fungal disease (IFD) which can be classified into one of five categories:

- Lomentospora (Scedosporium) prolificans (LoPro),
- Scedosporium spp.,
- Aspergillus spp.,
- Other F901318-susceptible fungi (as described in the Investigator Brochure [IB] or based on information provided by the Medical Monitor [MM], and in either case requiring approval of the MM), or
- Probable Lower Respiratory Tract Disease (LRTD) Invasive Aspergillosis (IA) based on the European Organization for Research and Treatment of Cancer/Invasive Fungal Infections Cooperative Group and the National Institute of Allergy and Infectious Diseases Mycoses Study Group (EORTC/MSG) criteria, but not meeting the criteria for culture proven invasive fungal infection.

Lifecycle Safety-CEVA Endpoint Adjudication Committee Charter documents these baseline categorization of IFD.

The first four categories require proven IFD. Diagnosis may be based on culture, polymerase chain reaction (PCR), or other acceptable methods. For patients with confirmed fungal infection no specific diagnosis method is required. The fifth category refers to probable LRTD IA, which must meet the EORTC/MSG criteria. All patients with IA must have galactomannan (GM) tests completed before enrolment. The initial diagnosis of IFD will be based on the Investigator assessment to minimise delays in treating patients. Disease categories will subsequently be assessed by an independent DRC. Patients with infections due to multiple fungi can be enrolled provided at least one fungus is known or predicted to be F901318-susceptible and the patient has limited alternative treatment options for that fungus as defined in Inclusion Criterion 7.

The study has two phases: the main study phase (Figure A) and the extended treatment phase (Figure B).

Up to and including protocol amendment 4 patients will receive a loading regimen of approximately 4 mg/kg of F901318 divided into two or three doses (12 or 8 hours apart respectively), followed by a maintenance regimen of approximately 2.5 mg/kg/day divided into two or three doses from Day 2 onwards. Based upon emerging data from studies in healthy volunteers, the recommended dose regimen may be revised to total daily dosages of up to 300 mg divided into two or three doses.

From protocol amendment 6 onwards patients will receive a one-day oral loading dose of 150 mg bid (dosed 12 ± 1 hours apart) followed by a maintenance dose regimen of 90 mg bid (dosed 12 ± 1 hours apart) from Day 2 onwards. Based upon clinical evaluation of efficacy by the Investigator, stepwise increases of maintenance doses of F901318 (to 120 mg bid, then 150 mg bid) may be permitted, following discussion with the MM.

Document: \\ieedc-vnasc01\BIOSdata\F2G\F901318\ [Redacted]
Author: [Redacted] Version Number: 3.0
Version Date: 06Apr2023
Template No.: CS_TP_BS016 Revision 6 Reference: CS_WI_BS005
Effective Date: 02Dec2019

[figure not shown]

F2G Ltd.
PROTOCOL F901318/0032

Patients will be treated until they reach a defined treatment endpoint. All patients should receive treatment for at least 14 days. Patients who are considered by the Investigator to have experienced a successful overall outcome will continue treatment with F901318 for at least seven days after resolution of all clinical signs and symptoms. The maximum duration of treatment in the main study phase will be 90 days. Patients judged to be a success on Days 78 to 83 (and hence requiring 85 to 90 days of total treatment) are eligible to receive up to 90 days of treatment in the main study phase. In addition, at the Investigator’s request and after discussion with the MM, open-label treatment with F901318 may be continued beyond Day 90 in patients who are considered likely to continue to benefit from extended treatment. In the case of patients proceeding to the extended treatment phase, the end of treatment (EOT) and end of study (EOS) are taken as the day therapy is completed in the main study phase. Patients in the main study phase who complete the EOT visit, will have a 4-week follow-up assessment 28 days after EOT. Patients in the extended treatment phase will not have the 4-week follow-up assessment 28 days after main study EOT, but will complete extended treatment phase follow-up visits on a four weekly basis, and a last visit four weeks after the end of extended treatment.

Figure A: Study flow diagram; main study phase

Abbreviations: EOT = End of Treatment; EOS = End of Study; ET = Extended Treatment; FU = Follow-Up; IA = Invasive Aspergillosis; LRTD = Lower Respiratory Tract Disease.

*EOS visit will be the last day the patient is in the main study phase. Note, however, the 4-week follow-up visit is not

Document: \\ieedc-vnasc01\BIOSdata\F2G\F901318 [Redacted]
 Author: [Redacted] Version Number: 3.0
 Version Date: 06Apr2023
 Template No.: CS_TP_BS016 Revision 6 Reference: CS_WI_BS005
 Effective Date: 02Dec2019

F2G Ltd.
PROTOCOL F901318/0032

necessarily the EOS for all patients as Day 42 and Day 84 are required for all patients (if successful outcome then required assessments will be performed; if unsuccessful outcome, then survival status will be obtained), if treatment is stopped prior to Day 42 or Day 84 the Day 42 and/or Day 84 may occur after the 4-week follow-up visit.

The Initial Clinical Study Report (CSR) will be prepared when 100 patients have completed the EOS visit in the main study phase (the first data cut-off date). The Initial CSR will include all main study phase data and available extended phase data for the 100 patients up to the first data cut-off date.

The Final CSR will be prepared at the end of the main study, defined as when the last patient has completed the EOS visit in the main study phase. The Final CSR will include follow-up for patients through to their main study phase EOS visit.

[figure not shown]

Data for those patients who have completed the EOS visit in the main study phase and have entered the extended treatment phase of the study will be displayed in narratives for the Initial CSR, Final CSR [redacted] analyses. Narratives will be produced by [redacted] Medical Writing and will include main study and extended treatment phase data.

Document: \\ieedc-vnasc01\BIOSdata\F2G\F901318 [redacted]
Author: [redacted] Version Number: 3.0
Version Date: 06Apr2023
Template No.: CS_TP_BS016 Revision 6 Reference: CS_WI_BS005
Effective Date: 02Dec2019

Figure B: Study flow diagram; extended treatment phase

Abbreviations: D = Day; EOT = End of Treatment; EOS = End of Study; ET = Extended Treatment; FU = Follow-Up; IA = Invasive Aspergillosis; LRTD = Lower Respiratory Tract Disease.

[Redacted text block]

3.2. SCHEDULE OF EVENTS

Schedule of events can be found in [section 4.1](#) of the protocol.

3.3. CHANGES TO ANALYSIS FROM PROTOCOL

- Protocol amendment 6 [section 8.9.4.3](#) states that changes in [Redacted]

[figure not shown]
[figure not shown]
Document: \\weedc-vnasc01\BIOSdata\F2G\F901318 [Redacted]
 Author: [Redacted] Version Number: 3.0
 Version Date: 06Apr2023
 Template No.: CS_TP_BS016 Revision 6 Reference: CS_WI_BS005
 Effective Date: 02Dec2019

[Redacted text block]

F2G Ltd.
PROTOCOL F901318/0032

- An additional listing was added to the analysis of Disposition ([section 9.1](#)) to present all patients whose trial participation was impacted by COVID-19 and to describe the particular impact.
- All protocol deviations relating to COVID-19 will in addition be summarised, and a by patient listing with the specific details will be provided.
- Protocol amendment 6 [section 8.7](#) states that Medications will be presented by Anatomical Therapeutic Chemical (ATC) class and Preferred Term. As the same Preferred Term occurs in more than one ATC term, it was decided to only present by ATC level 4, and not by Preferred Term as well.
- The per-protocol analysis set (PPAS) is added to SAP which was not mentioned in protocol amendment 6.
- Definition of Intensive PK set is modified in SAP from protocol amendment 6.
- “Summary tables of AST/ALT elevations in association with nausea, vomiting, anorexia, abdominal pain, fatigue” removed from SAP since it was not feasible to identify elevations in association with symptoms, and elevations and AESI are already thoroughly identified and summarized.
- “Patient-reported outcome  endpoint is not mentioned in protocol however it is added in SAP.
- Change in terminology “interim analysis” to “analysis for initial CSR”.
- Change in terminology 
- Summaries of serum GM by visit will be presented to assess changes in serum GM from baseline.

4. PLANNED ANALYSES

The following analyses will be performed for this study:

Document:	\\weedc-vnasc01\BIOSdata\F2G\F901318\ 		
Author:		Version Number:	3.0
		Version Date:	06Apr2023
Template No.:	CS_TP_BS016 Revision 6	Reference:	CS_WI_BS005
Effective Date:	02Dec2019		

- Analyses for Independent Data and Safety Monitoring Board (IDSMB) meetings
- Analyses for DRC meetings
- Analyses for the initial CSR
- Final Analysis
-

4.1. INDEPENDENT DATA & SAFETY MONITORING BOARD (IDSMB)

IDSMB output templates, portraying proposed data displays, will be provided by IQVIA Biostatistics as a separate document.

4.2. DRC ANALYSES

DRC patient profile output templates, portraying proposed data displays, will be provided by IQVIA Biostatistics as a separate document.

4.3. ANALYSES FOR INITIAL CSR

F901318 has been granted Breakthrough Therapy Designation by the Food and Drug Administration (FDA) based on preliminary clinical evidence that demonstrates F901318 may provide substantial improvement over available therapy. As this designation is intended to expedite the development and review of important products, an initial CSR analysis will take place for this study once 100 patients have completed the EOS visit in the main study phase.

The analyses used to support this Initial CSR analysis will include all main study phase data and available extended phase data for the 100 patients up to the point of the EOS visit in the main study.

Data for those patients who have completed the EOS visit in the main study phase and have entered the extended treatment phase of the study will be displayed in narratives for the Initial CSR. Limited safety data and efficacy endpoints for extended phase will be summarised. Narratives will be produced by Medical Writing and will include main study and extended treatment phase data.

Document: \\ieedc-vnasc01\BIOSdata\F2G\F901318

Author:	Version Number: 3.0
	Version Date: 06Apr2023
Template No.: CS_TP_BS016 Revision 6	Reference: CS_WI_BS005
Effective Date: 02Dec2019	

F2G Ltd.
PROTOCOL F901318/0032

Derivations and definitions for the initial analysis will be based on those required for the final analysis contained in this SAP, unless deviations are stated within the text. All outputs planned for the final analysis will be provided for the initial analysis.

4.4. FINAL ANALYSIS

All analyses identified in this SAP will be performed by [REDACTED] Biostatistics following F2G Ltd. authorisation of this SAP, database lock, and F2G Ltd. authorisation of analysis sets.

5. ANALYSIS SETS

Agreement and authorization of patients included/excluded from each analysis set will be conducted prior to the clinical database lock for the initial and final analyses of the study.

A Data Review (DR) plan will be created containing more details on the derivations of analysis sets and review of these by F2G Ltd.

5.1. PROCESS FOR ANALYSIS SET ASSIGNMENT

- Prior to clinical database lock for both initial and final analyses, data reviews will be performed to meet the following objectives:
 - Establish analysis set assignment.
 - Identify the potential reason(s) for exclusion of patients from one or more of the analysis sets. From a statistical perspective, the reason(s) for exclusion may be protocol deviations (identified during the clinical conduct of the study) or other factors affecting the efficacy outcome or treatment of the patient.
 - Identify underlying data issues affecting the integrity of the analyses on an ongoing basis during the clinical conduct of the study and to discuss any such issues impacting the efficacy analyses or requiring revision to the SAP prior to clinical database lock.
- A minimum of two weeks prior to each data review meeting the following will be delivered to IQVIA Biostatistics:
 - A clean snapshot of the database.

Document: \\ieedc-vnasc01\BIOSdata\F2G\F901318 [REDACTED]
Author: [REDACTED] Version Number: 3.0
Version Date: 06Apr2023
Template No.: CS_TP_BS016 Revision 6 Reference: CS_WI_BS005
Effective Date: 02Dec2019

F2G Ltd.
PROTOCOL F901318/0032

- The data handling report.
- The Clinical trials management system (CTMS) protocol deviation (PD) log (built up during the clinical conduct of the study and reviewed at scheduled protocol deviations review meetings; authorised prior to the final analysis clinical database lock).
- Any other information that may impact the decisions regarding the assignment of patients to the analysis sets.
- Biostatistics will then produce the following documents to be delivered to F2G Ltd. at least two business days prior to each data review meeting:
 - DR plan.
 - [Appendix 1: Assignment of Patients to Analysis Sets and Reason\(s\) for Exclusion \(EXCEL Spreadsheet\)](#).
- As part of the process of analysis set assignment Biostatistics will consider the following:
 - Analysis set definitions may be definitively determined algorithmically from the study database according to the rules.
 - Analysis set definitions may require supplemental data that does not form part of the clinical database to make assignment decisions; such information must be documented and authorised by F2G Ltd. prior to the final analysis clinical database lock.
 - In support of analysis set assignments a selection of by-patient data listings may be prepared and delivered to F2G Ltd. as part of data review package.
 - The data handling report, Biostatistics data issues log, CTMS PD log and other supplemental data may be considered in addition and may be delivered to F2G Ltd. as part of the data review package.
- During the data review meeting, Biostatistics will document the following in meeting minutes which can take the form of an EXCEL spreadsheet (recommended), report or actual meeting minutes document:
 - Decisions regarding analysis set assignment and reason(s) for exclusion of patients.
 - Decisions regarding data issues as identified in the data handling report and Biostatistics data issues log potentially impacting the planned analyses.

Document: \\ieedc-vnasc01\BIOSdata\F2G\F901318

Author: Version Number: 3.0
Version Date: 06Apr2023

Template No.: CS_TP_BS016 Revision 6 Reference: CS_WI_BS005

Effective Date: 02Dec2019

F2G Ltd.
PROTOCOL F901318/0032

- Patient-level decisions (for example, not to exclude a patient when an exclusion rule indicates the patient meets an exclusion criterion), with accompanying explanations.
- Following the data review meeting, [REDACTED] Biostatistics will follow up on actions as discussed at the data review meeting, for example additional data issues requiring query to sites.
- Once all outstanding actions items discussed during the data review meeting are resolved, [REDACTED] Biostatistics delivers the final data review report to F2G Ltd. for authorisation.
- After finalisation of the analysis set assignments (i.e. F2G Ltd. authorisation of the final data review report), [REDACTED] Biostatistics will add the analysis set flags and variable(s) indicating reason(s) for exclusion to the ADSL dataset.

5.2. ALL PATIENTS ENROLLED SET [ENR]

The all patients enrolled (ENR) set will contain all patients who provide written informed consent for this study.

5.3. INTENT-TO-TREAT SET [ITT]

The intent-to-treat (ITT) set will contain all patients in the ENR set who receive at least one dose of study medication.

5.4. MODIFIED INTENT-TO-TREAT [MITT]

The modified intent-to-treat (mITT) set will contain all patients in the ITT set who are assigned to a DRC-adjudicated disease category (see [Section 3.1](#), and process documented in DRC charter). The mITT population and sub-populations based on DRC-adjudicated disease categories will be used for the analysis of efficacy data.

5.5. PER-PROTOCOL ANALYSIS SET [PPAS]

The per-protocol analysis set (PPAS) will contain all patients in the mITT who complete the main study phase and have no major/critical protocol deviations during the main study phase that will impact the efficacy assessment. Protocol deviations will be reviewed on a case-by-case basis by the medical advisor to help determine the exclusions from the per-protocol set. Answers to inclusion/exclusion criteria will not be checked programmatically by [REDACTED] Biostatistics in consideration for exclusion from the PPAS. The responsibility for checking inclusion/exclusion criteria lies with Data Management.

Document: \\ieedc-vnasc01\BIOSdata\F2G\F901318 [REDACTED]
Author: [REDACTED] Version Number: 3.0
Version Date: 06Apr2023
Template No.: CS_TP_BS016 Revision 6 Reference: CS_WI_BS005
Effective Date: 02Dec2019

F2G Ltd.
PROTOCOL F901318/0032

Complete details on protocol deviations considered to impact efficacy and reasons for exclusion will be documented in the DR plan.

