*For these categories, the only required data are the clinical and mycological data. The absence of radiological evaluations at a given time point does not prevent assignment to Success-Complete or Success-Partial. The rules defining success are tested in sequence with Success-Complete assigned if its rules are met and Success-Partial otherwise assigned. The rules for Failure are tested next and Failure is assigned if any of its rules are met. The rules for Stable are tested last.

Number and % of patients will be summarised for the 4 categories shown in Table A. N and % will also be summarised for the 3 categories of Success (Success-Complete, Success-Partial), Stable disease (Failure-Stable) and Failure (Failure-Progression, Death, and those patients for whom data at Day 42 cannot be collected or who are considered not evaluable at Day 42).

For statistical primary analysis of overall response rate, values will be assigned to the DRC-adjudicated overall response as follows:

- Success (Success-Complete, Success-Partial),
- Failure (Failure-Stable, Failure-Progression, Death, and those patients for whom data at Day 42 cannot be collected or who are considered not evaluable at Day 42). Patients withdrawn from study medication due to an unsuccessful overall outcome are required per protocol to return for the main study phase EOT visit but will not be asked to return for the Day 42 and/or Day 84 visits; these patients will be considered as failures at all subsequent timepoints.

As a key important analysis, patients with a stable disease outcome will be considered a success, i.e. assigning the DRC adjudicated response to categories as follows.

- Success (Success-Complete, Success-Partial, Failure-Stable)
- Failure (Failure-Progression, Death, and those patients for whom data at Day 42 cannot be collected or who are considered not evaluable at Day 42)

This alternative classification, where stable disease outcome can be considered a successful response in the timeframe of this evaluation, is an important analysis due to the nature of this challenging patient population for whom other therapies have already failed.

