16.1.2. MISSING DATA METHODS FOR PRIMARY EFFICACY VARIABLE

Patients with a missing DRC-adjudicated overall response at Day 42 will be considered as failures.

Note: All mITT patients will be counted in the denominator of the %/ rate calculation at every visit through Day 84,

Document:	\\weedc-vnasc01\BIOSdata\F2G\F901318\		
Author:		Version Number:	3.0
		Version Date:	06Apr2023
Template No.:	CS_TP_BS016 Revision 6	Reference:	CS_WI_BS005
Effective Date:	02Dec2019		

even if they discontinue early.

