16.1.4. SENSITIVITY ANALYSIS OF PRIMARY EFFICACY VARIABLE

The primary efficacy analysis will be repeated for the PPAS.

Additionally, a sensitivity analysis of modified overall response will be performed for the mITT population where success will be defined as follows:

Modified Overall Response	Criteria
Success :	
• Clinical: Meets Criteria for Resolution-Complete or Resolution-Partial;• Radiological (if assessed): Shows no change or improvement of radiological abnormalities ($\geq 0\%$ response);• Mycological: Meets criteria for presumed or documented eradication.

The only required data are the clinical and mycological data. The absence of radiological evaluations at a given time point does not prevent assignment to Modified Overall Response as Success.

Similar to the primary analysis, a response rate will be calculated for the proportion of successes. A 95% exact Clopper-Pearson CI for the single binomial proportion will be calculated.

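### The per-protocol repeat of the Day 42 analysis admits only main-phase completers, so on the natural reading deaths by Day 42 drop out of it, with a net effect whose direction is not fixed

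*SAP*

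**What the plan says.** The PPAS is an SAP addition; SAP 3.3 records that the protocol does not mention it. Under SAP 5.5 the set will "contain all patients in the mITT who complete the main study phase and have no major/critical protocol deviations during the main study phase", where the deviations meant are those that affect the efficacy assessment. Completion and freedom from deviations are two separate conditions. SAP 16.1.4 then states: "The primary efficacy analysis will be repeated for the PPAS".

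The rule being repeated treats death and missing data as outcomes. SAP 16.1.1 defines the failure category as "Failure (Failure-Stable, Failure-Progression, Death, and those patients for whom data at Day 42 cannot be collected" or is not evaluable. Of patients withdrawn from study drug for an unsuccessful outcome, it says "these patients will be considered as failures at all subsequent timepoints". SAP 16.1.2 adds: "All mITT patients will be counted in the denominator of the %/ rate calculation at every visit through Day 84", early discontinuations included.

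The main phase runs well past Day 42. SAP 3.1 says: "The maximum duration of treatment in the main study phase will be 90 days". Neither document defines what it means to complete that phase. SAP 5 defers detail to a data review (DR) document: a "plan will be created containing more details on the derivations of analysis sets". SAP 5.1 also allows documented patient-level decisions, for example "not to exclude a patient when an exclusion rule indicates the patient meets an exclusion criterion".

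**The concern.** A per-protocol set is meant to remove departures from the protocol. Death from the infection is an outcome, not a departure. If completion is an entry condition and a patient who dies is not a completer, membership of the set depends partly on the endpoint it is used to estimate. It also depends on events after Day 42, because the phase to be completed is longer than the period to the endpoint.

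What is at stake is the reading of the sensitivity analysis. SAP 16.1.4 contains only two analyses: this one, and a modified response definition on the mITT. If the PPAS rate came out above the mITT rate, a reader could not tell robustness from the removal of deaths. If it came out close, a reader could not tell agreement from two exclusions that offset each other.

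**Working it through.** **No figure to reproduce.** The documents give no expected response, death or completion rate, and no expected PPAS size. Protocol 8.1 says that no formal sample size justification is possible. Everything below is therefore an illustration.

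**Inputs.**
- N = 200: planned enrolment (Protocol 8.1, SAP 3.1), used as an assumed mITT size.
- mITT success rate p = 30%, 40% or 50%: assumed.
- Deaths by Day 42, d = 10, 20 or 40 (5%, 10% or 20%): assumed. Protocol 2.3 cites about 20% six-week mortality for invasive aspergillosis on effective therapy, and more for resistant disease. Those are literature background, not expectations for this trial.
- Interval: exact Clopper-Pearson, as in SAP 16.1.3.
- No exclusions for protocol deviations.

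**Step 1: Day 42 deaths leave and nobody else does.** With S successes, the rate moves from S/N to S/(N − d). No patient who died by Day 42 is a success, so S does not change and the rate must rise.

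| mITT | d = 10 | d = 20 | d = 40 |
|---|---|---|---|
| 60/200 = 30.0% | 60/190 = 31.6% | 60/180 = 33.3% | 60/160 = 37.5% |
| 80/200 = 40.0% (33.2–47.1) | 80/190 = 42.1% (35.0–49.5) | 80/180 = 44.4% (37.1–52.0) | 80/160 = 50.0% (42.0–58.0) |
| 100/200 = 50.0% | 100/190 = 52.6% | 100/180 = 55.6% | 100/160 = 62.5% |

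**Step 2: x Day 42 successes also leave because they die or withdraw later.** The rate becomes (S − x)/(N − d − x). At p = 40% and x = 10:
- d = 10: 70/180 = 38.9% (31.7–46.4), below the mITT rate;
- d = 20: 70/170 = 41.2% (33.7–49.0), slightly above it.

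**Step 3: break-even.** Setting (S − x)/(N − d − x) = S/N gives x = d·p/(1 − p). At p = 40% this is 10 × 0.4/0.6 = 6.7 for 10 deaths and 13.3 for 20. If more successes than that leave later, the net effect is downward.

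**Step 4: the proposed rule.** With 20 Day 42 deaths and 10 later-leaving successes, keeping everyone and scoring at Day 42 gives 80/200 = 40.0%, equal to the mITT. Rescoring the 10 later-leaving successes as failures would give 70/200 = 35.0% (28.4–42.0), which is no longer a Day 42 analysis. Scoring therefore has to be fixed at Day 42.

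**Step 5: what completion could mean.**
- *Natural sense.* SAP 9.1 reports patients as either completed or prematurely withdrawn from the main study. A patient who died in the phase does not fit the first group.
- *Looser sense.* Protocol 8.13 starts the initial analysis once 100 patients have completed the main phase. Protocol 4.1 and SAP 3.1 and 4.3 state the same trigger as 100 patients completing the end-of-study (EOS) visit. Protocol 4.1 defines EOS per patient as the last assessment that patient completes. On this sense almost everyone completes.
- *Unsettled group.* Protocol 4.3.4 lists lack of efficacy and intolerable adverse events among reasons for withdrawal from drug and study. Yet Table 1 footnote b still expects the end-of-treatment (EOT) and follow-up (FU) visits from unsuccessful or withdrawn patients, with survival status at Days 42 and 84.

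**The case against.** The best counter-argument is the looser sense in Step 5. If completion in the initial-analysis trigger excluded deaths, the first 100 patients would all be survivors, which is implausible for an analysis that also reports mortality. Read that way in SAP 5.5, the condition would keep deaths in the PPAS. This stands as a second possible reading, but it does not rescue the wording: the condition would then exclude almost nobody and serve no purpose. The DR plan may settle the meaning, but it is not available, and case-by-case overrides in an open-label trial are a weak substitute for a stated rule.

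The consequence is also limited, and that stands in full. SAP 6 describes the analyses as generally descriptive, and no success threshold rests on the PPAS. The primary analysis and mortality use the mITT. SAP 9.1 has excluded patients listed and reasons summarised, so a reader can see who left.

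A reader might infer that the PPAS rate must be inflated, or that every patient withdrawn for lack of efficacy or an adverse event is certainly out. The documents support neither. Later-leaving successes pull the rate the other way, and the status of patients on the EOT/FU-only path is not defined.

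**Conclusion.** The point holds in a limited form. SAP 5.5 sets a completion condition that, on the natural reading, takes deaths by Day 42 out of a repeat of an analysis that counts them as failures. That component can only raise the rate: by 2.1, 4.4 or 10.0 percentage points from 40.0% if 5%, 10% or 20% of 200 patients die by Day 42. The net effect can go either way, as the fall to 38.9% shows. On the looser reading the condition does almost nothing. On neither reading should it stand as written.

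The sizes rest on assumed response and death rates and an assumed mITT of 200. The conclusion about the wording does not depend on them. It should be corrected, but it affects one descriptive sensitivity analysis and leaves the primary result untouched.

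**What to change.** In SAP 5.5, delete the requirement to complete the main study phase. The PPAS is then the mITT patients with no major or critical deviation affecting efficacy. Leave the deviation window as it is: SAP 16.1.7.1 makes the secondary overall-response analyses similar to the primary one, so a window cut to Day 42 could admit unsuitable patients if the PPAS repeat is carried to EOT or Day 84.

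State that every member is scored by SAP 16.1.1 and 16.1.2. Death, unsuccessful withdrawal, or a missing or non-evaluable response by Day 42 counts as failure. A Day 42 success who leaves later stays a success.

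If a completion condition is kept, state that death, withdrawal for lack of efficacy or an adverse event, and the EOT/FU-only path do not by themselves remove a patient from the Day 42 PPAS analysis.

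The cost is SAP wording and a fresh check of set assignments; no new data or tables are needed. The PPAS rate may change, in a direction that depends on who would have been excluded. If the initial analysis has already used the present definition, the final report should note the change.
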